6. ADVERSE EVENTS: LIST AND REPORTING REQUIREMENTS

6.1 Safety Analysis

Safety will be analyzed for patients treated in this study. All patients who receive any amount of study drug will be evaluable for toxicity.

At each visit, a brief focused history will be obtained and any indication of treatment-related toxicity will be evaluated by appropriate examination and/or laboratory/radiographic studies.

Safety analyses will include summaries of adverse event rates and changes in laboratory results, as well as number of CTCAE (v4.0) toxicity grades for both laboratory and non-laboratory data.

The evaluation period should extend from date of first treatment until 100 days from discontinuation of treatment, and until resolution from all acute toxicities associated with the drug administration.

6.2 Definition of Adverse Event Terms

Adverse Event: Any unfavorable and unintended sign (including an abnormal laboratory finding), symptom, or disease temporally associated with the use of a medical treatment or procedure regardless of whether it is considered related to the medical treatment or procedure (attribution of unrelated, unlikely, possible, probable, or definite). [NIH Guidelines, January 2001]

Serious Adverse Event (SAE): Any adverse drug experience occurring at any dose that results in any of the following outcomes:

- 1) Death
- 2) A life-threatening adverse drug experience
- 3) In-patient hospitalization or prolongation of existing hospitalization
- 4) Any persistent or significant disability/incapacity
- 5) A congenital anomaly/birth defect
- 6) Is a new cancer (that is not a condition of the study)
- 7) Is associated with an overdose
- 8) Is another important medical event
- 9) Pregnancy

Important medical events that may not result in death, be life-threatening, or require hospitalization may be considered a serious adverse drug experience when, based upon appropriate medical judgment, they may jeopardize the patient and may require medical or surgical intervention to prevent one of the outcomes listed in this definition. [Code of Federal Regulations Title 21].

Progression of the cancer under study is not considered an adverse event unless it results in hospitalization or death.

“Serious” Versus “Severe” Adverse Events: There is a distinction between serious and severe AEs. Assessment of seriousness will be made solely by the serious criteria listed above.

Severity of AEs will be graded according to the NCI Common Terminology Criteria for Adverse Events v4.0. Therefore, serious events will not be automatically considered severe. For example, a stroke that results in only a limited degree of disability may be considered a mild (not severe) stroke, but it would still meet serious criteria and thus, be captured as an SAE. Similarly, severe events may not always be serious. An example would be an episode of severe, transient nausea which persists for

several hours. This would be classified as a “severe” episode of nausea, but if it did not require treatment, intervention, or somehow meet other serious criteria, it would not be considered an SAE.

Life-threatening Adverse Drug Experience: Any adverse drug experience that places the patient or subject, in the view of the investigator, at immediate risk of death from the reaction as it occurred, i.e. it does not include a reaction that, had it occurred in a more severe form, might have caused death. [21CFR312.32(a)]

Unexpected Adverse Drug Experience: Any adverse drug experience, the specificity or severity of which is not consistent with the current investigator brochure; or, if an investigator brochure is not required or available, the specificity or severity of which is not consistent with the risk information described in the general investigational plan. “Unexpected” as used in this definition, refers to an adverse drug experience that has not been previously observed rather than from the perspective of such experience not being anticipated from the pharmacological properties of the pharmaceutical product.

Laboratory test abnormalities: Laboratory abnormalities that constitute an adverse event in their own right (are considered clinically significant, induce clinical signs or symptoms, require concomitant therapy or require changes in study treatment), should be recorded. Whenever possible, a diagnosis, rather than a symptom should be provided (e.g. anemia instead of low hemoglobin). Laboratory abnormalities that meet the criteria for adverse events should be followed until they have returned to normal or an adequate explanation of the abnormality is found. When an abnormal laboratory or test result corresponds to a sign/symptom of an already reported adverse event, it is not necessary to separately record the lab/test result as an additional event.

Laboratory abnormalities, that do not meet the definition of an adverse event, should not be reported as adverse events. A Grade 3 or 4 event (severe) as per CTCAE does not automatically indicate a SAE unless it meets the definition of serious as defined below and/or as per investigator’s discretion. Please note that a dose hold or medication for a lab abnormality may be required by the protocol in which case the lab abnormality would still, by definition, be an adverse event and must be reported as such.

6.3. Toxicity Grading

Toxicities will be graded according to the current version of the NCI Common Terminology Criteria for Adverse Events (CTCAE) Version 4.0. The full text of the NCI CTCAE is available online at: <http://ctep.cancer.gov/forms/CTCAEv4.pdf>

If a certain event or symptom is not described in the CTCAE grades, use the following grading scale:

| | |
|--------------------|---|
| Mild | Awareness of event, but easily tolerated |
| Moderate | Discomfort enough to cause some interference with usual activity |
| Severe | Inability to carry out usual activity |
| Very Severe | Debilitating, significantly incapacitates patient despite symptomatic therapy |

6.4. Toxicity Attribution

Assessment of attribution is made by consideration of all clinically relevant data prior to, during, and after occurrence of the event, including diagnostic tests to assess the cause of the event.

Clinically relevant data include, but are not limited to; underlying disease, past and present medical history (all concurrent non-malignant disease), concurrent medications, and timing between event and drug administration. The mechanism of action and prior toxicology of the study drug should be considered.

An adverse event is associated with the use of the drug when there is a reasonable possibility that the experience may have been caused by the drug. Potential attribution of an adverse event associated with trial therapy will be provided for all study drugs, nivolumab and/or ipilimumab.

Attribution Standards per NCI – CTEP:

Unrelated The Adverse Event is clearly not related to the investigational agent (s)

Unlikely The Adverse Event is doubtfully related to the investigational agent(s)

Possible The Adverse Event may be related to the investigational agent(s)

Probable The Adverse Event is likely related to the investigational agent(s)

Definite The Adverse Event is clearly related to the investigational agent(s)

6.5. Yale Principal Investigator Safety Reporting Requirements

6.5.1 Expedited Reporting of Unexpected SAEs

AEs classified as “serious” and “unexpected” that are possibly, probably, or definitely attributed to drug administration, or SAEs whose frequency exceeds expectations, require expeditious handling and reporting.

The PIs will promptly investigate all safety information related to an adverse experience. If the results of the PIs’ investigation show an adverse drug experience not initially determined to be reportable (based on whether the event is serious, unexpected, and associated with drug administration) is so reportable, the PIs will report such experience. Follow-up information to a safety report shall be submitted as soon as the relevant information is available.

6.5.2 Reporting to the Yale Human Investigation Committee

All SAEs, whether originating at Yale or a collaborating center, meeting the criteria for expedited reporting will be reported to the Yale University Human Investigation Committee (HIC) using HIC Form 710 FR 4: Unanticipated Problem Involving Risks to Subjects or Others (UPIRSOs), including Adverse Events (AEs) Reporting Form as per IRB Policy 710.

The HIC does not require reporting of any other Adverse Event type. A copy of the IRB Policy 710 Reporting Unanticipated Problems Involving Risks to Subjects or Others, including Adverse Events is available at:

http://www.yale.edu/hrpp/policies/documents/NewIRBPolicy710_UPIRSOSAE_4.3.2014_withflowchart_vF.PDF

6.5.3 Reporting to the Food and Drug Administration

This study will be conducted under an IND (Investigational New Drug application) that will be held by the Principal Investigator, [name]. The Principal Investigator will report in an expedited manner all SAEs meeting the criteria of “serious”, “unexpected” and “related to study treatment”. Written safety reports will use a MedWatch Form 3500A. A “fillable pdf” version with

instructions is available at: http://www.fda.gov/medwatch/safety/FDA-3500A_Fillable_08-16-2006.pdf

There are two types of expedited safety reports to the FDA:

1. 7-Calendar-Day FDA Telephone or Fax Report: The sponsor-investigator will directly notify the FDA, within 7 calendar days after his initial receipt of the information, of any adverse event that is ALL of the following:

- Death or immediately life-threatening
- Unexpected
- Associated with the use of nivolumab or ipilimumab

Notification to the FDA will be made directly to the new drug review division in the Center for Drug Evaluation and Research or in the product review division for the Center for Biologics Evaluation and Research, whichever was responsible for the review of the IND. [21CFR312.32(c)] A written report of the event is to follow within 15 calendar days.

2. 15-Calendar-Day FDA Written Report: The sponsor-investigator will directly notify the FDA within 15 calendar days of any adverse event that is ALL of the following:

- Serious (due to non-fatal and non-life threatening criteria)
- Unexpected
- Associated with the use of nivolumab or ipilimumab

Note: Serious Adverse Events which do not meet the criteria for expedited reporting will be reported to the FDA in the IND Annual Report.

6.5.4 Reporting to Bristol Myers Squibb

Investigators must report all SAEs to Bristol Myers Squibb within the timelines described below. The completed MedWatch/case report should be faxed and/or emailed immediately upon completion to BMS Drug Safety at:

SAE [contact]**

SAE Email Address: **[contact]**

Relevant follow-up information should be submitted to BMS Drug Safety as soon as it becomes available.

SAE reports whether related or unrelated to nivolumab or ipilimumab will be transmitted to BMS within 24 hours of the Awareness Date.

Additional reporting requirements to BMS include the following:

- Any reports of pregnancy following the start of administration of nivolumab and within the follow-up period (for female patients within 5 months after the last dose of nivolumab or ipilimumab or the partner of a male patient within seven months of completing therapy) will be transmitted to BMS within 24 hours of the Awareness Date.
- All non-serious nivolumab or ipilimumab AEs originating from the study will be forwarded to BMS quarterly

Follow-Up Information

Additional information may be added to a previously submitted report by any of the following methods:

- Adding to the original MedWatch 3500A report and submitting it as follow-up
- Adding supplemental summary information and submitting it as follow-up with the original MedWatch 3500A form
- Summarizing new information and faxing it with a cover letter including patient identifiers (i.e., D.O.B. initial, patient number), protocol description and number, if assigned, brief AE description, and notation that additional or follow-up information is being submitted. (The patient identifiers are important so that the new information is added to the correct initial report.)

Occasionally BMS may contact the reporter for additional information, clarification, or current status of the patient for whom and AE was reported. Relevant follow-up information should be submitted to BMS Drug Safety as soon as it becomes available and/or upon request.

6.5.5. Duration of Reporting of SAEs

From the administration of first treatment until 90 days (unless otherwise specified) subsequent to last treatment or withdrawal of subject, new onset adverse events will be captured. Follow-up and reporting of these events will follow the same procedure as for AEs observed during the study period. In addition, any unexpected Serious Adverse Event that occurs more than 90 days after drug administration but is possibly, probably or definitely attributed to drug administration will be recorded and reported.

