1.2. Secondary Objectives/ Endpoints

- A. To determine the objective response rate (ORR) using immune related Response Criteria (irRC) to nivolumab and ipilimumab when administered in combination to patients with pre-treated advanced NSCLC who have experienced primary resistance to anti-PD-1 axis therapy as their last line of systemic therapy.
- B. To determine progression-free (RECIST v1.1 and irRC) and overall survival with nivolumab and ipilimumab when administered in combination to patients with pre-treated advanced NSCLC who have experienced primary resistance to anti-PD-1 axis therapy as their last line of systemic therapy.
- C. To determine ORR and progression free survival (PFS) by RECIST v1.1 and irRC, and overall survival, in patients with pre-treated advanced NSCLC who have experienced acquired resistance to anti-PD-1 axis therapy as their last line of systemic therapy
- D. To characterize the safety profile of nivolumab and ipilimumab when administered in combination, and feasibility of sequential biopsies, in patients with pre-treated advanced NSCLC who have experienced primary or acquired resistance to anti-PD-1 axis therapy as their last line of systemic therapy
- E. To evaluate changes in the tumor microenvironment and blood after adding ipilimumab to anti- PD-1 axis therapy in patients with primary and acquired resistance to anti-PD-1-axis as their last line of systemic therapy

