4.8.3. Monitoring

Safety will be evaluated in this study through the monitoring of all serious and non-serious AEs, defined and graded according to NCI CTCAE v4.0. (see appendix 1). Patients will be assessed for safety (including laboratory values) according to Section 5. Patients will be followed for safety for 100 days following the last dose of study treatment.

General safety assessments will include serial interval histories, physical examinations, and specific laboratory studies, including serum chemistries and blood counts (see Section 5 for the list and timing of study assessments). All SAEs and protocol-defined events of special interest (see Section 6) will be reported in an expedited fashion (see Section 6.5). In addition, investigators will review and evaluate observed AEs on a regular basis.

Patients who have an ongoing study treatment-related adverse event upon study completion or at discontinuation from the study will be followed until the event has resolved to baseline grade, the event is assessed by the investigator as stable, new anti-cancer treatment is initiated, the patient is lost to follow-up, the patient withdraws consent, or until it has been determined that study treatment or participation is not the cause of the AE.

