5.3. Follow-up Visits

All patients who discontinue the study treatment will have a follow up visit at Day 28 ±7 days from the last study treatment.

- 1) History and physical examination
- 2) Measurement of height, weight and vital signs (including blood pressure, heart rate, respiratory rate, oxygen saturation, and temperature).
- 3) Performance status evaluation
- 4) Review concomitant medications
- 5) Adverse events assessment
- 6) CBC with differential, serum chemistry (Na, K, Cl, CO₂, BUN, creatinine, glucose, calcium), magnesium, phosphate, liver function tests (albumin, total protein, alkaline phosphatase, total, ALT, AST), LDH, and TSH with reflex free T4 and free T3
- 7) Tumor assessment with CT scan of the chest/abdomen/pelvis and brain every 9 weeks (+/- 5 days) until progression, withdrawal of consent, death, lost to follow-up, or start of a subsequent anti-cancer therapy

All patients who discontinue early or who complete the study treatment period will be followed for survival. Survival follow-up information will be collected via telephone calls, patient medical records, and/ or clinic visits every 3 months +/- 14 days until death, loss to follow-up or study termination. All patients will be followed for survival unless the patient requests to be withdrawn from follow-up. If the patient withdraws from study treatment but not from follow-up, the study staff may use a public information source to obtain information about survival status.

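### Section 6.5.5 ends general adverse-event capture at 90 days, while Sections 4.8.3 and 6.1 run safety follow-up and evaluation to 100 days; separately, no adverse-event assessment is scheduled after the Day 28 visit

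*Combined protocol and SAP*

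**What the plan says.** Three sections of the protocol set a post-treatment safety period.

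- Section 4.8.3 (Monitoring): "Patients will be followed for safety for 100 days following the last dose of study treatment". The same section refers to Section 5 for the safety assessments themselves.
- Section 6.1 (Safety Analysis): "The evaluation period should extend from date of first treatment until 100 days from discontinuation of treatment", and further until acute toxicities resolve.
- Section 6.5.5 (Duration of Reporting of SAEs): "until 90 days (unless otherwise specified) subsequent to last treatment or withdrawal of subject, new onset adverse events will be captured". After that it adds only "any unexpected Serious Adverse Event that occurs more than 90 days after drug administration but is possibly, probably or definitely attributed to drug administration".

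The heading of 6.5.5 mentions SAEs, but its text covers all new-onset adverse events.

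On scheduling, Section 5.3 says that patients who stop treatment "will have a follow up visit at Day 28 ±7 days from the last study treatment", and an adverse-event assessment is listed for that visit. Scans then continue every 9 weeks until progression or another stopping event. In addition, "Survival follow-up information will be collected via telephone calls, patient medical records, and/ or clinic visits every 3 months +/- 14 days". Neither of these later contacts lists an adverse-event assessment. The study calendar (Section 5.4) has one end-of-treatment column and nothing after it.

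Safety is part of secondary objective D (Section 1.2): "To characterize the safety profile of nivolumab and ipilimumab when administered in combination, and feasibility of sequential biopsies". Section 9 tabulates on-study adverse events by worst grade but gives no day on which on-study ends.

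**The concern.** A collection rule should cover at least the period that will be analysed. Here the section that tells sites how long to record new events stops 10 days before the period over which safety is to be evaluated. A site working from 6.5.5 and a site working from 4.8.3 would record different sets of events, and Section 9 does not tell the analyst which to use.

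The second matter is independent of the first. Whichever window applies, the schedule contains no planned occasion to ask about adverse events after roughly day 28. Later events would enter the database only if the patient or a treating clinician happened to report them.

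At stake are the completeness and consistency of a descriptive secondary result. Response rate, sample size and the stopping rule are not involved.

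**Working it through.** There is no planned figure to reproduce. The check compares the texts and counts days.

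**Inputs**

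| Item | Source | Value | Counted from |
|---|---|---|---|
| General capture of new-onset events | 6.5.5 | 90 days | last treatment or withdrawal |
| Safety follow-up | 4.8.3 | 100 days | last dose |
| Safety evaluation period | 6.1 | 100 days, and until acute toxicities resolve | discontinuation of treatment |
| Last listed adverse-event assessment | 5.3 | Day 28 ±7 (21 to 35) | last study treatment |
| Planned patients | 4.1 | 40 + 10 = 50 at most | – |

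**Step 1: gap between collection and evaluation, common start date.** 100 − 90 = 10 days, that is days 91 to 100.

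**Step 2: which events fall in the gap.** Unexpected SAEs attributed to drug are still recorded under the last sentence of 6.5.5. Treatment-related events already ongoing at discontinuation are followed further under 4.8.3. What remains is new-onset non-serious events, expected SAEs, and SAEs not attributed to drug.

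**Step 3: sensitivity to the start date.** The three texts use three different starting points. As an illustration, suppose withdrawal or discontinuation is dated 14 days after the last dose, one nivolumab interval (Section 4.3).

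- 6.5.5 counted from withdrawal ends at 14 + 90 = day 104 after the last dose. That is past the 100 days of 4.8.3.
- 6.1 counted from discontinuation ends at 14 + 100 = day 114, so a gap of 114 − 104 = 10 days remains.
- If 6.5.5 is counted from last treatment instead, the gap to 6.1 is 114 − 90 = 24 days.

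The 10-day figure therefore holds only for a common start date.

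**Step 4: time without a scheduled assessment.** From the Day 28 visit to day 100 is 100 − 28 = 72 days. With the visit window it is 100 − 35 = 65 to 100 − 21 = 79 days. Against a 90-day window it would be 90 − 28 = 62 days (55 to 69).

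**Step 5: can the 3-monthly contact close the window?** Section 5.3 does not say what the interval is counted from. Taking 3 months as about 91 days:

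- from the last dose, the contact falls on days 91 ± 14 = 77 to 105;
- from the Day 28 visit, it falls on days 28 + 91 ± 14 = 105 to 133.

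On the first reading the contact may take place before day 100, so its timing would have to be stated.

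**The case against.** The strongest reply is that 6.5.5 is only a default. It yields where another section specifies otherwise, and 4.8.3 and 6.1 both specify 100 days. This has some force, and it makes the text ambiguous rather than flatly contradictory. It does not settle the matter: 6.5.5 has no cross-reference, and its last sentence switches to a narrower rule after 90 days without repeating the qualifier. If 100 days governed, that sentence would be wrong for days 91 to 100.

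A second reply is that Section 6.5.4 sends all SAEs, related or not, to the manufacturer within 24 hours and gives no end date. That may catch some SAEs in the gap, but it covers SAEs only, and it leaves open how it fits with 6.5.5.

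Several stronger readings are tempting and should not be drawn.

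- A reader might infer that the safety analysis itself has two cut-offs. It does not: no analysis text uses 90 days, and 6.1 gives a single period. The mismatch is between collection and evaluation.
- A reader might link the Day 28 visit to that mismatch. It does not cause it; it is a separate gap in ascertainment.
- A reader might take 10 of 100 days to mean that 10% of events are lost. A share of days is not a share of events, and some event types are still captured.
- A reader might argue that late-onset immune events make the gap serious. Section 4.8.4 says that events with these agents can differ in severity and duration; it does not say that they start late after treatment ends.

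**Conclusion.** The point holds as a mismatch between what is collected and what is evaluated, together with a separate gap in scheduled ascertainment. Read literally and from a common start date, 6.5.5 leaves days 91 to 100 without general capture of new-onset non-serious events and of expected or unattributed SAEs, although 6.1 includes those days. About 72 days (65 to 79) of the 100-day window have no scheduled adverse-event assessment, for at most 50 patients. Patients without progression still attend for scans in that time, but no adverse-event assessment is listed for those contacts.

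The conclusion assumes that the qualifier in 6.5.5 does not import the 100 days, which the text leaves open. How many events would be missed cannot be worked out from the documents. The effect is confined to the descriptive safety objective, but the correction is small and should be made.

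**What to change.** 1. Reconcile Sections 4.8.3, 6.1 and 6.5.5 to one window and one start date. Collection in 6.5.5 should cover the whole evaluation period in 6.1 (100 days as now written), for adverse events and SAEs alike. The closing sentence of 6.5.5 should then take effect from the end of that window.
2. Define on-study adverse events in Section 9 by the same window and start date.
3. In Sections 5.3 and 5.4, add adverse-event questions to the first 3-monthly follow-up contact. Specify it as direct contact with the patient, counted from the last dose, and made at or just after the end of the window.

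This is slightly more than a change of wording. Section 5.3 now lets survival information come from medical records, so no call is guaranteed; under the change, records review alone would no longer satisfy the first contact. A few more adverse events would have to be recorded. No extra clinic visit is needed, and the sample size and primary analysis do not change.
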